## 5.5 Pulmonary Toxicity

In the event of a new onset of dyspnea, persistent cough, or other pulmonary symptoms while on study treatment, and there is a concern for drug-induced interstitial lung disease, study treatment should be stopped until the subject can be adequately evaluated;

dose modification is not appropriate in this setting. Subjects should be counseled throughout study treatment to alert the investigator or designated team member immediately if they develop new or worsening respiratory symptoms.

For subjects with any new or worsening cough or dyspnea of unknown etiology (with or without fever), or unexplained symptoms or radiological findings suggestive of interstitial lung disease, testing should minimally include: measurement of oxygen saturation by pulse oximetry and chest CT. Drug-induced pneumonitis is a diagnosis of exclusion, therefore investigators must thoroughly evaluate subjects who demonstrate potential signs/symptoms of pneumonitis/pneumonia. If a subject has a potential diagnosis of pneumonitis or drug-related lung injury the following evaluations/procedures should be considered to assist or exclude the diagnosis of pneumonitis during this period:

- A sputum gram stain and culture (induced sputum if needed) bacterial, viral, fungal, protozoal, and mycobacteria;
- Human immunodeficiency virus testing;
- Blood culture if the subject is febrile;
- Thoracentesis if pleural fluid is present (examined for same pathogens as sputum);
- Bronchoscopy with bronchoalveolar lavage if appropriate. The bronchoalveolar lavage fluid should be sent for culture and cytology (same pathogens as above);
- Lung biopsy (e.g., open or thorascopic if preferable, bronchoscopy with transbronchial biopsy) if appropriate based on the subject's clinical status. Video-assisted thoracoscopy may be considered to acquire tissue via a minimally-invasive procedure;
- A plasma sample for B-type natriuretic peptide (BNP) to check for any evidence of chronic heart failure;
- If clinically appropriate, high dose corticosteroid treatment should be initiated.

Should the event be fatal, an autopsy is highly recommended to confirm/exclude the

diagnosis. For any case of suspected pneumonitis, it is concluded that a thorough investigation has excluded treatment-induced pulmonary toxicity, study treatment may resume.

## **5.6 Drug supplies and storage**

Lorlatinib will be supplied as 100mg and 25 mg tablets for oral administration. Lorlatinib will be dispensed at the beginning of each treatment cycle (or as otherwise indicated). Patients should be instructed to keep their medication in the bottles provided and not transfer it to any other container.

The investigator, or an approved designee (e.g., pharmacist), will ensure that all study drug is stored in a secured area, under recommended storage conditions (lorlatinib: controlled room temperature) and in accordance with applicable regulatory requirements. Under no circumstances should the investigator or other site personnel supply study drug to other investigators, subjects, or clinics, or allow supplies to be used other than directed by this study. Adequate records documenting receipt, use, return, loss, or other disposition of tablets must be kept. The drug provider may supply drug accountability forms that will be used, or may approve use of standard institution forms. The forms must identify the investigational product, including batch numbers, and account for its disposition on a subject by subject basis, including specific dates and quantities. The forms must be signed by the individual who dispensed the drug, and copies must be provided to CRO Medical upon request.

Tablets must be administered according to the study directions. The reason for missed doses should be entered on the CRF to ensure adequate records. All study drugs will be accounted for in the CRF and drug accountability inventory forms as instructed by the Sponsor. All bottles or blister cards (either used or unused) must be returned to the investigator by the subject. Unless otherwise authorized at the end of the study, all drug supplies unallocated or unused by the subjects must be returned to the provider or its appointed agent.

## **5.7 Selection and Timing of Dose for Each Patient**

Patients were instructed to take their study treatment at approximately the same time every day, or as close as possible to the same time every day, with the following exception: for protocol-required delays (such as on specified study visit days), patients were instructed not to take their medication until after they had undergone any scheduled pre-dose assessments in the clinic and had been evaluated by the investigator for continuation of therapy.

Patients were instructed not to make up missed doses of study treatment, but rather to simply resume the regular dosing schedule on the day following a missed dose. Likewise, patients were instructed not to make up for a vomited dose by taking an extra dose the same day, but rather to resume the regular dosing schedule the next day as prescribed. Any missed or vomited doses were recorded in the source documents and eCRFs, just as all administered doses were documented.

Medication errors including those that involved patient exposure to the study product and potential medication errors or uses outside of what was foreseen in the study protocol that did or did not involve the participating patient, were reported on the AE eCRFs irrespective of the presence of an associated AE or SAE.

## **5.8 Prior/Concomitant Medications and Treatments**

All concomitant medications should be recorded in the CRF including supportive care drugs (e.g., antiemetic treatment and prophylaxis), and the drugs used to treat adverse events or chronic diseases, and non-drug supportive interventions (e.g., transfusions). Medications intended solely for supportive care (e.g., antiemetics, analgesics, megestrol acetate for anorexia, bisphosphonates or RANK-ligands for metastatic bone disease or osteoporosis) are allowed. In case the patient is already on treatment with RANK-ligands (like denosumab) before study entry, the therapy should be at a stable dose prior to randomization.

### **5.8.1. Inhibitors and Inducers of CYP Enzymes**

The in vitro studies have demonstrated that CYP3A, and UGT1A4 are primarily involved in the metabolism of lorlatinib, with additional minor contributions from CYP2C19 and CYP2C8. Inhibition or induction of the above enzymes may result in potential alteration of lorlatinib systemic exposure.

Initial in vitro assessment for inhibition and induction drug-drug interaction potential indicated that lorlatinib is a time-dependent inhibitor of CYP3A and also an inducer of CYP3A and CYP2B6. At substantially higher concentrations than those observed clinically, lorlatinib also inhibited CYP2C9 in in vitro studies.

To protect patient safety, the following cautions are provided:

- Lorlatinib metabolism may be inhibited by strong CYP3A inhibitors leading to a potential increase in lorlatinib toxicities. Coadministration of strong CYP3A inhibitors (e.g., boceprevir, cobicistat, conivaptan, itraconazole, ketoconazole, and posaconazole, ritonavir alone and with danoprevir or elvitegravir or indinavir or lopinavir or paritaprevir or ombitasvir or dasabuvir or saquinavir or tipranavir, telaprevir, troleandomycin, and voriconazole, grapefruit juice or grapefruit/grapefruit-related citrus fruits [e.g., Seville oranges, pomelos]) is not recommended and alternate medications should be considered. If the concomitant use of the strong CYP3A inhibitor cannot be avoided, reduce the starting dose of lorlatinib from 100 mg orally once daily to 75 mg orally once daily. In patients who have had a dose reduction to 75 mg orally once daily due to adverse reactions and who initiate a strong CYP3A inhibitor, reduce the lorlatinib dose to 50 mg orally once daily. The patient should be closely monitored for safety and reduction of the lorlatinib dose if necessary. If concomitant use of a strong CYP3A inhibitor is discontinued, increase the

lorlatinib dose (after 3 plasma half-lives of the strong CYP3A inhibitor) to the dose that was used before starting the strong inhibitor.

- Use of strong CYP3A inducers with lorlatinib is contraindicated.  
Lorlatinib metabolism may be induced when taking strong CYP3A inducers (e.g., carbamazepine, enzalutamide, mitotane, phenytoin, rifampin, St. John's Wort) resulting in reduced plasma concentrations. Furthermore, when lorlatinib was coadministered with rifampin, increases in AST and ALT were noted. Discontinue strong CYP3A inducers for 3 plasma half-lives of the strong CYP3A inducer prior to initiating lorlatinib and until study treatment discontinuation. In addition, use with moderate CYP3A inducers (e.g., bosentan, efavirenz, etravirine, modafinil) should be avoided due to the potential reduction in lorlatinib exposure.
- Lorlatinib induces CYP2B6 (in vitro) so concurrent use of drugs that are CYP2B6 substrates, such as bupropion and efavirenz, may have less effect. Concomitant CYP2B6 substrates should be used with caution, as the net clinical effect of lorlatinib on CYP2B6 is currently being investigated.
- Lorlatinib induces CYP3A (in vivo) which may lead to a decreased effect of concurrently used CYP3A substrates (e.g., hormonal contraceptives etc.).  
Coadministration of lorlatinib with CYP3A substrates with a narrow therapeutic index (NTI) such as alfentanil, fentanyl (including transdermal patch), astemizole, cisapride, cyclosporine, dihydroergotamine, ergotamine, pimozide, quinidine, sirolimus, tacrolimus, terfenadine is not permitted at study entry. However if it is absolutely necessary to use, sponsor approval is required and the dose of the CYP3A substrate may need to be increased. The NTI CYP3A substrate should be started only

after at least 14 days of continuous lorlatinib dosing. If there is a change in the lorlatinib dosing regimen such as a dosing interruption or dose reduction, the administration of the NTI CYP3A substrate should be stopped and resumed at a readjusted dose only after at least 14 days of resumed lorlatinib dosing.

- Lorlatinib inhibits P-glycoprotein (P-gp) (in vitro) so concurrent use of drugs which are P-gp substrates with a narrow therapeutic index may have increased effect. The concurrent use of drugs which are P-gp substrates with narrow therapeutic index, such as digoxin is not permitted at study entry. The use of these drugs during the study is not recommended and alternate medications should be considered. If absolutely necessary to use during the study, it should be initiated following sponsor approval, and be used then with caution. The net clinical effect of lorlatinib on P-gp is currently being investigated.

Any questions regarding the use of alternative medications should be directed to the Investigator for guidance.

## **5.9 Other Anti-Tumor/Anti-Cancer or Experimental Drugs**

The concurrent use of select vitamins or herbal supplements is not permitted.

## **5.10 Other Prohibited Concomitant Medications and Therapies**

Patients are prohibited from receiving the following therapies during the treatment phase of this trial:

1. Investigational agents other than lorlatinib.
2. Other experimental pharmaceutical products.

3. Herbal remedies with anticancer properties or known to potentially interfere with major organ function or study drug metabolism (e.g., hypericin).

## **5.11 Hematopoietic Growth Factors**

Use of granulocyte colony stimulating factors should follow the current American Society of Clinical Oncology (ASCO) guidelines. Patients who enter the study on stable doses of erythropoietin or darbepoetin may continue this treatment, and patients may start either drug during the study at the discretion of the investigator.

## **5.12 Supportive Care**

Subjects who are receiving bone modifying agents to control pain/bone metastases as recommended in current guidelines for bone-targeted therapy (e.g. bisphosphonates or denosumab) may continue while on therapy but initiation of such a therapy after enrolment will be considered progression of disease unless otherwise agreed by the investigator in consultation with the Sponsor.

Palliative radiotherapy for painful bony lesions is permitted providing the lesions were known to be present at the time of study entry and the investigator clearly indicates the need for palliative radiotherapy is for better palliation than alternative analgesic options, and is not due to disease progression.

# **6. STUDY PROCEDURES**

All assessments and procedures during the study are detailed in the Schedule of Activities (**Table 1**).

To allow for subject and investigator schedules, holidays, and weather or other emergencies requiring clinical facilities to be closed, all subject visits can be performed within -4/+2 days of the scheduled visit date. To allow for additional flexibility in scheduling subject visits and procedures, screening and baseline procedures may be completed on the same day. In that case, treatment must start one day after screening/baseline procedures but within three days. Baseline and Cycle 1 Day 1 procedures may be completed on the same day. However, screening assessments for *eligibility* MUST have already been completed by the preceding day. Screening, baseline, and Cycle 1 Day 1 cannot be completed all together on the same day.

## 6.1 Pre-screening and Informed Consent

Patients with the following will be pre-identified:

- Subjects who have newly diagnosed stage IB, II, IIIA or selected IIIB (including T4N2, per AJCC 8th edition) resectable non-squamous NSCLC;
- Subjects with an ALK-rearrangement mutation based on assessment as part of the standard of care for this disease;
- Subjects who have adenocarcinoma or its pathologically accepted variants.

Subjects meeting the above criteria must provide written informed consent prior to any study-specific procedures being performed.

## 6.2 Screening

All screening assessments are to be performed within 28 days prior to first study drug administration of lorlatinib. Assessment conducted prior to informed consent and within 28 days of first dose (Cycle 1 Day 1) can be used as data for screening. To establish subject eligibility for subsequent treatment, the following assessments will be completed:

- Confirm evidence of newly diagnosed stage IB, II, IIIA or selected IIIB (including T4N2, per AJCC 8th edition) resectable non-squamous NSCLC, allowable methods of disease measurement is PET/CT. The decision on which area of the body to be imaged is as determined by investigator judgment.
- Confirmation of ALK rearrangement via Ventana D5F3, NGS, etc. testing methods by local laboratory. Ventana D5F3 is recommended for reconfirmation in NGS and other testing methods;
- Vital signs, body weight and height will be measured (see Section 7.3.3);
- ECOG PS (see [Appendix 1](#));
- Blood and urine samples will be collected (hematology, blood chemistry, coagulation, pregnancy test (female subjects with reproductive potential), urinalysis; see Section 7.3.2);
- A 12-Lead ECG reading will be performed with attention to QTc interval, with Fridericia's or Bazett's correction for abnormal heart rate as applicable (see Section 7.3.1);
- Prior/concomitant medication and SAE data will be collected. This would include the drug name, start/stop dates and indication.

### 6.3 Baseline

The following text outlines baseline assessments and procedures to be performed (see Schedule of Activities **Table 1**).

Within 2 weeks prior to Cycle 1 Day 1, the following assessments will be performed. It is unnecessary to repeat assessment at baseline if screening assessment and all laboratory evaluation items for baseline were performed at screening and within 2 weeks prior to Cycle 1 Day 1 (Pregnancy test result need to be known to be negative prior to study treatment: In case of serum sample, pregnancy test needs to be conducted within 72 hours prior to Cycle 1 Day 1. In case of urine sample, pregnancy test needs to be conducted on Cycle 1 Day 1 before study treatment is started.) and there is no clinical reason to believe the baseline has significantly changed:

- Vital signs and body weight will be measured (see Section 7.3.3);
- Demographics and medical history (relevant clinical events and conditions including tumor-related signs and symptoms); collection of subject reported weight loss over the past 6 months; history of smoking;
- Physical examination will be performed;
- A 12-Lead ECG reading will be done. QTc must be less than CTCAE v5.0 Grade 2 ( $\leq 480$  msec) using Fridericia's or Bazett's correction formula with a manual reading by the investigator if required. The ECG may be repeated for evaluation of eligibility after management of correctable causes for observed QTc prolongation (see [Section 7.3.1](#)). Subject whose heart rate  $<45$  beats per minute in the presence of clinical symptoms (e.g., hypotension, evidence of hypoperfusion) will not start study treatment;
- Blood samples will be collected (hematology, blood chemistry, coagulation and pregnancy test; see Section 7.3.2;
  - a. Estimated creatinine clearance  $\geq 30$  mL/min (as determined by Cockcroft-Gault formula or the study site's standard formula);
  - b. Absolute neutrophil count (ANC)  $\geq 1500$  cells/mm^3;
  - c. Platelets  $\geq 100,000$  cells/mm^3;
  - d. Hemoglobin  $\geq 9.0$  g/dL;
  - e. Bilirubin  $\leq 1.5 \times$  ULN;
  - f. AST (also known as SGOT) and ALT (also known as SGPT)  $\leq 2.5 \times$  ULN ( $\leq 5.0 \times$  ULN if hepatic metastases);
- Prior/concomitant medication and SAE data will be collected and reviewed;

Subjects who sign the informed consent, and successfully completed screening and baseline assessments will subsequently be assigned open label lorlatinib. Treatment must start within 3 days.

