### 4.1 Inclusion Criteria

Subjects must meet all the following inclusion criteria to be eligible for enrollment into the study:

- Male or female subjects who are  $\geq 18$  years of age
- Histologically or cytologically documented non-squamous surgically resectable stage IB, II, IIIA or selected IIIB NSCLC (including T4N2, per AJCC 8th edition)
- Clinical stage IB, II, IIIA or selected IIIB assessed PET/CT that can be resected
- Documented ALK-rearrangement positive (assessed by a local laboratory)
- Performance status (ECOG) 0-1 at enrolment, with no deterioration over the previous 2 weeks prior to baseline or day of first dosing of lorlatinib
- Hematology, liver and kidney function are adequate for induction therapy.
  - Adequate Bone Marrow Function, including:
    - a. Absolute Neutrophil Count (ANC)  $\geq 1,500/\text{mm}^3$  or  $\geq 1.5 \times 10^9/\text{L}$ ;
    - b. Platelets  $\geq 100,000/\text{mm}^3$  or  $\geq 100 \times 10^9/\text{L}$ ;
    - c. Hemoglobin  $\geq 9 \text{ g/dL}$ .
  - Adequate Pancreatic Function, including:
    - a. Serum total amylase  $\leq 1.5 \times$  upper limit of normal (ULN)\*;

b. Serum lipase  $\leq 1.5 \times$  ULN.

\*if total amylase  $> 1.5 \times$  ULN, but pancreatic amylase is within the ULN, then patient may be enrolled.

- Adequate Renal Function, including:

a. Serum creatinine  $\leq 1.5 \times$  ULN or estimated creatinine clearance  $\geq 60$  mL/min as calculated using the method standard for the institution.

- Adequate Liver Function, including:

a. Total serum bilirubin  $\leq 1.5 \times$  ULN;

b. Aspartate Aminotransferase (AST) and Alanine Aminotransferase (ALT)  $\leq 2.5 \times$  ULN ( $\leq 5.0 \times$  ULN in case of liver metastases).

- Cardiopulmonary function suitable for surgical treatment (ECG, echocardiography, pulmonary function or blood gas analysis).
- Be willing and able to provide written informed consent for the trial prior to any study specific procedures. The subject must also provide consent for correlative translational study.
- Female participants of childbearing potential must agree to use acceptable methods of contraception
- Male patients must be willing to use barrier contraception.
- Serum pregnancy test (for females of childbearing potential) negative at screening. Female patients of non-childbearing potential must meet at least 1 of the following criteria:

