## **4.2 Exclusion Criteria**

Subjects presenting with any of the following characteristics/conditions will not be included in this clinical study:

- Mixed squamous cell carcinoma, large cell carcinoma, small cell lung cancer.
- Prior treatment with any systemic anti-cancer therapy for NSCLC including chemotherapy, biologic therapy, immunotherapy, or any investigational drug.
- Pregnant female patients; breastfeeding female patients.
- Malignancies other than the disease under study within 3 years prior to Cycle 1, Day 1, with the exception of patients with a negligible risk of metastasis or death and with expected curative outcome
- Severe infection within 4 weeks prior to initiation of study treatment, including but

not limited to hospitalization for complications of infections, or any active infection that, in the opinion of the investigator, could impact participant safety

- Pregnant or lactating, or intending to become pregnant during the study
- Concurrent enrolment in another clinical study, unless it is an observational (non-interventional) clinical study or during the follow-up period of an interventional study.
- Active and clinically significant bacterial, fungal, or viral infection including hepatitis B virus (HBV) or hepatitis C virus (HCV) (e.g., in case of known HBsAg or HCV antibody positivity), known human immunodeficiency virus (HIV), or acquired immunodeficiency syndrome (AIDS)-related illness.
- Clinically significant vascular (both arterial and venous) and non-vascular cardiac conditions, (active or within 3 months prior to enrollment), which may include, but are not limited to:
  - a. Arterial disease such as cerebral vascular accident/stroke (including Transient Ischemic Attack -TIA), myocardial infarction, unstable angina;
  - b. Venous diseases such as cerebral venous thrombosis, symptomatic pulmonary embolism;
  - c. Non-vascular cardiac disease such as congestive heart failure (New York Heart Association Classification Class  $\geq$  II), second-degree or third-degree AV block (unless paced) or any AV block with PR  $>220$  msec; or ongoing cardiac dysrhythmias of NCI CTCAE Grade  $\geq 2$ , uncontrolled atrial fibrillation of any grade, bradycardia defined as  $<50$  bpm (unless patient is otherwise healthy such as long-distance runners, etc.), machine-read Electrocardiogram (ECG) with QTc  $>470$  msec, or congenital long QT syndrome.

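### Section 6.3 sets baseline limits for QTc, heart rate and renal function that differ from the eligibility limits in Section 4, and does not refer back to Section 4

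*Protocol*

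**What the plan says.** The protocol sets numeric entry limits in Section 4 and again in Section 6.3, the baseline check before Cycle 1 Day 1.

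- **QTc.** Section 4.2 lists as an exclusion "machine-read Electrocardiogram (ECG) with QTc $>470$ msec, or congenital long QT syndrome". Section 6.3 says "QTc must be less than CTCAE v5.0 Grade 2", given as 480 msec or below, using Fridericia's or Bazett's correction and a manual reading by the investigator if required. It also allows the ECG to be repeated to judge eligibility once correctable causes have been dealt with.
- **Heart rate.** Section 4.2 excludes "uncontrolled atrial fibrillation of any grade, bradycardia defined as" below 50 bpm, with an exemption for otherwise healthy patients. Section 6.3 withholds the start of treatment only for a rate below 45 "beats per minute in the presence of clinical symptoms".
- **Renal function.** Section 4.1 requires serum creatinine of at most 1.5 × ULN, or an estimated clearance of at least 60 "mL/min as calculated using the method standard for the institution". Section 6.3 requires at least 30 "mL/min (as determined by Cockcroft-Gault formula or the study site's standard formula"), with no creatinine alternative.

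The closing paragraph of Section 6.3 then assigns lorlatinib to consented patients who have successfully completed screening and baseline. It does not mention Section 4.

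**The concern.** Section 6.3 is the last check before the first dose, and it looks like a list of eligibility limits. For neutrophils, platelets, hemoglobin, bilirubin and AST/ALT it repeats the figures of Section 4.1. For QTc, heart rate and renal function it gives other figures without saying why. A list that agrees on five parameters and differs on three reads more like unreconciled text than a deliberate second tier.

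These are cardiac and renal safety limits in a protocol that has its own rules for QTc prolongation (Table 3) and heart block (Table 4). Six sites are planned. If some work from Section 4 and others from Section 6.3, the same patient could be turned away at one and dosed at another, and the second case would be an eligibility deviation.

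**Working it through.** No figure in the protocol needs reproducing here. The check sets each pair of rules side by side and finds the values on which they disagree (QTc and heart rate in whole units, the same reading put through both rules).

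| Parameter | Section 4 | Section 6.3 | Fails Section 4, passes 6.3 | Passes Section 4, fails 6.3 |
|---|---|---|---|---|
| QTc | excluded if > 470 msec (machine) | accepted if ≤ 480 msec (manual if required) | 471–480 msec | none |
| Heart rate, not exempt | excluded if < 50 bpm | barred if < 45 bpm and symptomatic | 45–49 bpm with or without symptoms; < 45 bpm without symptoms | none |
| Heart rate, exempt as otherwise healthy | not excluded | barred if < 45 bpm and symptomatic | none | < 45 bpm with symptoms |
| Renal | creatinine ≤ 1.5 × ULN **or** clearance ≥ 60 mL/min | clearance ≥ 30 mL/min | creatinine > 1.5 × ULN with clearance 30–59 mL/min | creatinine ≤ 1.5 × ULN with clearance < 30 mL/min |

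**Can the renal bands occur?** Section 6.3 names the Cockcroft-Gault formula: clearance = (140 − age) × weight / (72 × creatinine), times 0.85 for women. The protocol gives no creatinine ULN, so I assume 1.0 to 1.3 mg/dL. The two patients are invented for illustration.

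- Man, 60 years, 70 kg, creatinine 0.1 mg/dL above 1.5 × ULN. At ULN 1.0: 80 × 70 / (72 × 1.6) = 48.6 mL/min. At ULN 1.3: 80 × 70 / (72 × 2.05) = 37.9 mL/min. He fails 4.1 and passes 6.3 over the whole assumed range.
- Woman, 85 years, 40 kg, creatinine at the ULN. At ULN 1.0: 55 × 40 × 0.85 / (72 × 1.0) = 26.0 mL/min. At ULN 1.3: 55 × 40 × 0.85 / (72 × 1.3) = 20.0 mL/min. She passes 4.1 and fails 6.3.

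**Could the two sections be meant for different measurements?** Not necessarily. Section 6.3 waives a repeat at baseline when the screening assessments and all the baseline laboratory items were done within two weeks before Cycle 1 Day 1 and nothing suggests a relevant change. The opening of Section 6 allows screening and baseline on the same day. A single ECG reading 475 msec can therefore be the one that Section 4.2 excludes and Section 6.3 accepts.

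**Which QTc reading decides?** Section 4.2 names the machine reading. Section 6.3 allows a manual one if required. Section 7.3.1 says a prolonged electronic reading has to be confirmed manually. Section 4.2 does not say what happens if the machine shows more than 470 msec and the manual reading does not.

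**The case against.** The strongest reply is that Section 4 governs and Section 6.3 only adds conditions. The text supports this. Section 4.1 requires every inclusion criterion to be met, and Section 4.2 keeps out anyone with any listed condition. The opening of Section 4 has eligibility reviewed and documented before inclusion. Section 5.1, in an incomplete sentence, refers to patients who have met the criteria. Section 6 requires eligibility screening to be finished by the day before treatment. The limits in 6.3 are also worded as bars, not permissions.

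A reader might infer that Section 6.3 allows dosing of a patient whom Section 4 excludes. The documents do not support that: passing 6.3 is necessary for dosing, not sufficient, and giving lorlatinib at a QTc of 475 msec would breach Section 4.2.

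Three further replies carry some weight.

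- The renal rules partly complement each other. Because Section 4.1 is an either-or rule, reading it as a flat 60 against 30 mL/min would overstate the conflict. The floor in 6.3 adds a bar that 4.1 lacks.
- The difference between machine and manual reading may explain part of the QTc gap. The numeric limits still differ.
- Section 5.4 describes the ECG changes seen with lorlatinib as confined to the PR interval, and Section 4.1 separately requires cardiopulmonary function fit for surgery. Both temper the practical concern.

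What stands is that Section 6.3 describes its repeat ECG as a check of eligibility, uses its own numbers, and leads to treatment assignment without pointing to Section 4. A joint reading settles what is permitted; it does not stop a site from working from the wrong list.

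**Conclusion.** The protocol contradicts itself on three safety entry limits. The conflict covers QTc 471–480 msec, the heart-rate combinations tabulated above, and two combinations of creatinine and clearance. It runs in one direction for QTc and in both for heart rate and renal function.

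The consequence is limited. Section 4 binds, so the exposure is to eligibility deviations and uneven practice across sites, not to a sanctioned route around the exclusions. That sites would in fact differ is a risk inferred from the wording; the protocol does not show it.

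A reader might also infer that the trial's result is at stake, since enrolled patients stay in the full analysis set of Section 9.2.1. The protocol gives no frequency for patients in the conflict bands, and nothing in it shows an effect on the pCR decision. The case for acting is patient safety and consistent eligibility. No view is taken here on which limit is right.

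**What to change.** 1. Reconcile Section 6.3 with Sections 4.1 and 4.2 so that QTc, heart rate and renal function each have one limit. If two tiers are intended, state expressly that the 6.3 conditions apply in addition to Section 4.
2. State whether the machine or the manual QTc reading decides eligibility, consistently with Section 7.3.1.
3. Have Section 6.3, including its closing paragraph on treatment assignment, refer to the Section 4 criteria.

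The sponsor chooses the limits. The cost is an amendment of wording; sample size, endpoints and analysis are unchanged.
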